Based on the pilot study we assumed an 88% consent rate per arm; this will leave approximately 57-60 participants from which we will need to recruit 50 per arm. We also accounted for 6% attrition in 3 months.

1.1. Change in Secondary Measures of Cognitive Function Over 6 Months. We will use a linear mixed model approach to describe the 3- and 6-month change in secondary cognitive function measures. We will construct a base model by fitting a single slope after enrollment. We will include two random effects: intercept and time relative to enrollment. This will allow for a unique trajectory for each participant, which varies randomly around the trajectory described by the fixed effects. The estimate for the time since enrollment variable will quantify the magnitude of the change in executive and global cognitive function (pre- and post-intervention) associated with CT, ET, and CT+ET. We will explore non-linear functions of time through cubic splines. The model is:

$$(CF_{ij} - CF_{i0}) = [\beta_{00} + \beta_{1i} \text{time}_{ij} + \beta_{01} X_i + \beta_{11} X_i (\text{time}_{ij})] + [b_{0i} + b_{1i} (\text{time}_{ij})] + r_{ij} + \varepsilon_{ij}$$

where time is time since enrollment, and X is the vector of interventions. We recognize that mortality may occur during the study and those who are survivors may be a distinct population and there may be differential mortality by intervention. If we find evidence for this differential survival, we will account for the unobservable executive and global cognitive function after death by 1) creating a composite endpoint that ranks mortality as worse than any change in executive or global cognitive function (composite endpoint), and 2) generate a causal model for change regardless of mortality using a survival-averaged causal effect model. As a sensitivity analysis, we will test that our findings are robust to the analytic approach using global z-scores.

2.0. Analytic Methods: Effect of CT, ET, and CT+ET on ESRD-specific clinical outcomes.

Staff at NYU Langone Health will help with data analysis. Data will be shared through a HIPAA Compliant Johns Hopkins REDCap database. The NYU Langone Health team will be conducting data analysis for all components of this study and requires all variables to do so.

2.1. Time to Event Outcomes: Mortality. To examine the univariate association between study arm and mortality, separate product-limit estimated cumulative incidence curves will be calculated. Next, we will use a Cox proportional hazards model to estimate the association of study arm with time to the development of mortality. Censoring will occur at loss to follow-up or KT. The hazard function for the Cox model is:

$$\lambda(t|X_i) = \lambda_0(t) \exp(X_i \beta)$$

where x_i is the value of the covariate X for the i th participant, and $\lambda_0(t)$ is the baseline hazard function. If the proportional hazards assumption is not met, we will include an interaction with time.

2.2. Dichotomous Outcomes: Poor Lower Extremity Function, poor HRQOL, return to work, and amputation. We will test whether the study arm is associated with poor lower extremity function, poor HRQOL, return to work, and amputation using logistic regression or a modified Poisson regression (145), if the outcome is $>10\%$.

2.3. Count Outcomes: Number of Falls and Hospitalizations. We will use Poisson regression to test whether the study arm is associated with the number of falls and hospitalizations within the 3 months of the intervention.

3.0. Analytic Methods: Effect of CT, ET, and CT+ET on patient-centered outcomes.

Change in Patient-centered Outcome: For each patient-centered outcome, we will calculate a score. We will treat each patient-centered outcome as continuous and will estimate the change in these outcomes between baseline and 3 months. We will analyze each patient-centered outcome separately. We will analyze the change in these outcomes using the analytic plan described in 1.0.

3.1. Change in Patient-centered Outcome over 6 Months. Patient-centered outcomes are longitudinal data (3 and 6 months) and analyzed using the analytic plan described in 2.0 for repeated measures of executive function.

4.0. Treatment Effect Heterogeneity. Frailty has been associated with worse trajectories of executive function in older adults (146) and HD patients (16). Therefore, we will explore treatment heterogeneity between those who are frail and nonfrail in all primary and secondary outcomes. We will include an interaction term between frailty status and intervention type (study arm) to assess difference in treatment effect by frailty status. Using a similar approach, we will test for treatment effect heterogeneity by age, sex, and race/ethnicity.

Risks:

Risk from Cognitive Training Intervention:

Participants in the CT arm may feel tired or bored from playing similar cognitive games. They may feel frustrated if they are trying to learn new games and are unsuccessful with the games. Participants may develop a headache due to eyestrain from focusing on the tablet screen. All participants will be encouraged to wear their reading glasses while performing the CT if applicable.

Risk from Exercise Training Intervention:

Participants in the ET arm may experience fatigue, exhaustion, discomfort, muscle soreness, pain or cramping in the legs from using the foot peddler. Participants may experience shortness of breath, a change in heart rate or blood pressure while performing the activity.

Risk from Frailty Measurements and Physical Function Assessments:

Participants may experience fatigue or exhaustion from performing the grip strength, chair stands, balance and walk speed.

Risk from Quality of Life and Health Questionnaires:

Participants may experience fatigue, exhaustion, emotional discomfort or boredom from answering the questionnaires.

Minimization of Risks:

All participants will go through an eligibility screening process. We will enroll only those who meet all of the inclusion criteria and none of the exclusion criteria. The treating nephrologist is required to give permission for a patient to enroll in the study to ensure it is safe for them to participate.

All participants will sign an IRB-approved informed consent. We will inform them that participation is strictly voluntary and that they may decline to continue participation in the study at any time point, discontinue the assessments during the session, or refuse to answer any questions they do not want to. At the start of each session, we will inform the participants in the CT, ET, and CT+ ET arms that they are free to stop the activity at any time if they feel any discomfort or for some other reason cannot continue. Additionally, physicians, nurse practitioners, and dialysis staff will be on staff during the session to help monitor the participants health while undergoing hemodialysis and participating in the study.

The study team will make every effort to protect the participants' privacy by conducting interviews and assessments in an area at the dialysis center that is not within earshot or view of other clinic patients.

Confidentiality and Risk Protection:

We will keep all data collected strictly confidential so there is minimal risk of loss of confidentiality. All participating faculty and staff have received appropriate training in the responsible conduct of research, protection of human subject participants, and HIPAA regulations. All data collection instruments and consent forms will be kept in a locked cabinet. All questionnaires, assessments and cognitive function data will be stored in RedCap, a secured database. To maximize confidentiality, only the study investigators, data manager and key study personnel will have access to the information.

Data Safety Monitoring Board (DSMB) and Adverse Event Reporting:

An independent DSMB will be established to oversee the safety and progress of this trial, comprised of five individuals (a patient advocate, an ethicist, a statistician, a nephrologist, and a research nurse) who will serve in this capacity throughout the entirety of the trial. We will ensure that all members of the DSMB disclose of any conflicts of interest. The DSMB will have pertinent experience and review accumulating data from this RCT on a regular basis with the goal of enhancing the safety of the trial participants. A DSMB is warranted in this RCT because the study is being performed in a potentially vulnerable population, namely those with ESRD on HD and this population is at elevated risk of serious outcomes. A medical monitor will be included on the DSMB to review all events and determine whether they classify as AE's/ or SAE's.

We will monitor the number of injurious falls resulting in a medical encounter during the 6 months of interventions. This data will be obtained during the survey portion of our assessments by asking the participant to self-report the number of falls in the last 6 months. Additionally, falls during the intervention or assessment will be directly observed and recorded by study staff. Any falls will be reported to the medical monitor for review and determination whether they classify as an AE or SAE attributable to the interventions.

The DSMB will be identified and managed through the ICTR and will be established and operated using the Guidance put forth by the US Food and Drug Administration "Guidance for Clinical Trial Sponsors: Establishment and Operation of Clinical Trial Data Monitoring Committees" (<https://www.fda.gov/downloads/RegulatoryInformation/Guidances/ucm127073.pdf>). The DSMB will be local and managed by the ICTR to allow for quick convening of meetings in the event of an unexpected result that raises concerns.

None of these individuals will be involved in the design or conduct of the trial. Any unanticipated problem or adverse event will be reported as outlined in JHU IRB policy 103.6(b). When possible the DSMB will be blinded to the study arm.

If any SAEs are more common in one of the three intervention arms compared to the standard of care arm, then the DSMB will consider termination of the study if the risks outweigh the benefits for participants. All SAEs that are deemed to have a causal relationship with the interventions in one of the arms of the study will be reviewed by the DSMB for the consideration of patient safety.

Planned DSMB Reviews:

The Data and Safety Monitoring Board (DSMB) shall review safety data during planned DSMB Data Review Meetings when 10%, 25%, and 50% of enrolled participants have completed 3 months of interventions and to analyze and review the interim analyses of these adverse events during active data collection. Data for the planned safety reviews will include, at a minimum, a listing of all reported AEs and SAEs. The DSMB will be informed of an Expedited Safety Report in a timely manner. The DSMB will have a final meeting at the end of the study.

We have performed a comprehensive literature search of published and unpublished manuscripts to identify possible side effects, adverse events, and serious adverse events of CT and ET interventions. No adverse events were noted in the literature search for side effects, adverse events or serious adverse events for CT. We theorize that the two most common risks associated with CT are the following: 1) boredom 2) frustration and 3) headache.

There are greater risks associated with the ET intervention than with the CT intervention. The main risks associated with ET include: 1) Hypotension or low blood pressure which can cause dizziness and fainting. Hypotension can frequently occur during hemodialysis due to fluid removal. Hypotension is the most common risk of intradialytic ET and can occur in up to 33% of dialysis sessions in which exercise is involved, 2) cramping, muscle soreness, pain and fatigue, and 3) dyspnea or shortness of breath which occurs commonly during exercise. While hypertension and elevated heart rate were not noted as a risk associated with ET, we will also consider hypertension as a possible risk. Blood pressure reading of SBP>150 or DBP>90 mmHg will be considered as hypertension. SBP<110 or DBP<50 mmHg will be considered as hypotension. Heart rate that is consistently >80% of maximum heart rate will be considered as elevated.

Ad Hoc DSMB Reviews

In addition to the pre-scheduled data reviews and planned safety monitoring, the DSMB may be called upon for ad hoc reviews. The DSMB will review any event that potentially impacts safety at the request of the PI or NIDDK representative. In addition, the following events will trigger an ad hoc comprehensive DSMB Safety Review:

- Any death in the study which is considered possibly or definitely related to a study procedure.
- If any of the following adverse events occur at a significant higher rate than expected in the CT, ET, or CT+ET arm: muscle cramping, hypotension, or headache. We have outlined thresholds for pausing rules for rates of cramping, hypotension, hypertension, elevated heart rate, or headache which will trigger a mandatory pause in study enrollment for an unscheduled Data Safety and Monitoring Board review.

Cramping/Muscle Soreness: At the first day of each month, we will perform a Bayesian analysis of the ratio of cramping rates between ET arm (or CT+ET arm) versus the SC group. We will use a prior distribution of beta for each subgroup. We will then analyze the ratio of the distributions using a Monte

Carlo simulation. If there is 75% chance that [rate of cramping in the ET arm or CT+ET arm] divided by [rate of cramping in the SC arm] exceeds 1.10 (10% more in ET arm or CT+ET arm), we will pause the study pending DSMB recommendation.

Hypotension: we will perform a Bayesian analysis of the ratio of hypotension rates between ET arm (or CT+ET arm) versus the SC arm. We will use a prior distribution of beta(0,0) for each subgroup. We will then analyze the ratio of the distributions using a Monte Carlo simulation. If there is an 75% chance that [rate of hypotension in the ET arm or CT+ET arm] divided by [rate of hypotension in the SC arm] exceeds 1.15 (15% more in ET arm or CT+ET arm), we will pause the study pending DSMB recommendation.

Hypertension: At the first day of each month, we will perform a Bayesian analysis of the ratio of hypertension rates between ET arm (or CT+ET arm) versus the SC arm. When calculating hypertension rates, we will exclude dialysis sessions with starting blood pressure being hypertensive. We will use a prior distribution of beta(0,0) for each subgroup. We will then analyze the ratio of the distributions using a Monte Carlo simulation. If there is an 75% chance that [rate of hypertension in the ET arm or CT+ET arm] divided by [rate of hypertension in the SC arm] exceeds 1.15 (15% more in ET arm or CT+ET arm), we will pause the study pending DSMB recommendation.

Elevated Heart Rate (EHR): At the first day of each month, we will perform a Bayesian analysis of the ratio of EHR rates between ET arm (or CT+ET arm) versus the SC arm. We will use a prior distribution of beta (0,0) for each subgroup. We will then analyze the ratio of the distributions using a Monte Carlo simulation. If there is an 75% chance that [rate of EHR in the ET arm or CT+ET arm] divided by [rate of EHR in the SC arm] exceeds 1.08 (8% more in ET arm or CT+ET arm), we will pause the study pending DSMB recommendation.

Headache: At the first day of each month, we will perform a Bayesian analysis of the ratio of headache rates between CT arm (or CT+ET arm) versus the SC arm. We will use a prior distribution of beta(0,0) for each subgroup. We will then analyze the ratio of the distributions using a Monte Carlo simulation. If there is an 75% chance that [rate of headache in the CT arm or CT+ET arm] divided by [rate of headache in the SC arm] exceeds 1.12 (12% more in CT arm or CT+ET arm), we will pause the study pending DSMB recommendation.

After review of the data, the DSMB will make recommendations regarding study conduct and/or continuation.

Temporary Suspension of enrollment for Ad Hoc DSMB Safety Review

A temporary halt in enrollment at all participating centers will be implemented if an ad hoc DSMB safety review is required.

Benefits:

There is no direct benefit to the participants for being in the study. However, there is a possibility of a direct benefit from the participants having access to a cognitive training regime or an exercise training regime. There are no direct benefits to participants randomized to the standard of care arm. All study participants may help providers and other patients in the future by contributing to the knowledge base for performing interventions for patients undergoing hemodialysis.

Payment and Remuneration:

All participants will receive a \$10 gift card after completion of study assessments at baseline. Participants in the standard of care arm will receive a \$25 gift card after completion of assessments at 3 months, and at 6 months. Participants in the CT, ET, or CT+ET arms will receive a \$10 gift card after completion of study assessments at 3 months and at 6 months. Additionally, participants in the intervention arms will receive \$5 for each HD session they engage in their assigned intervention. Participants will not receive compensation if they withdraw from the study. Travel or other expenses will not be reimbursed as all the assessments and activities related to the study will be conducted during their regularly scheduled hemodialysis appointment at the dialysis center.

Costs:

There are no costs to the participant for being in the study.

Coordinating Site Information:

Johns Hopkins will serve as the coordinating center. NYU has an active FWA and OHRP on file that the Johns Hopkins IRB has worked with successfully in the past. The Johns Hopkins PI, [name], and [name] the site lead at NYU will be in frequent contact and address any protocol changes or amendments. All data will be entered into a secure REDCap database and managed by [name] at NYU. There will be no changes to data management at Johns Hopkins. The NYU study team will provide the JH study team with any necessary information for annual continuing reviews. The PI will be responsible for education to sites about JHM policies and oversight of protocol events, deviations, and ensuring appropriate reporting. The NYU Langone Health study team will analyze and collect data for this study. To ensure data collection is consistent across sites, that longer term follow-up can be performed, and re-contact for future studies, all data collected over the course of the trial must be shared. All data will be shared over a HIPAA compliant Johns Hopkins secure REDCap data base. We will add NYU study team members to the Johns Hopkins REDCap project in order for them to access any necessary data. Access to the data at NYU will be restricted to only study team members. We will use a Data Access Group created by Johns Hopkins IT to add NYU personnel to the REDCap project. Only authorized personnel will be able to add additional team members to the project after they are added to the IRB.

REFERENCES

1. United States Renal Data System, 2016 Annual Data Report: Atlas of Chronic Kidney Disease and End-Stage Renal Disease in the United States. Bethesda: National Institute of Diabetes and Digestive and Kidney Diseases, 2016.
5. Spreen O, Spreen E. A compendium of neuropsychological tests: Administration, norms and commentary. 2nd ed. New York: Oxford University Press.

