Summary of Significance: There is a high burden of ESRD in the US and most patients undergo time-intensive HD treatment during which interventions could be administered. Replacing passive intradialytic activities with cognitively beneficial activities is a missed opportunity. CT and ET are the only two effective non-pharmacological interventions to preserve executive function, which is supported by our pilot data. The findings from this RCT will provide nephrologists who care for the vulnerable population of HD patients with the first feasible and effective interventions for their patients who are at risk for experiencing executive function decline. Interventions are needed to target the prevention of executive function decline, rather than simply attempting to reverse decline or regain executive function.

Study Procedures

This is a 2 by 2 factorial randomized controlled trial (RCT). We will randomize participants to CT alone, ET alone, both CT+ET, or SC resulting in four arms. Randomization will be achieved through balancing methods over the three stratification factors: study center, sex, and race/ethnicity.

Study Population: Men and women with ESRD and receiving maintenance HD 2-3 times weekly at one of the 13 hemodialysis centers participating in the trial will be eligible. We will only enroll new HD patients, as has been done in other RCTs (89-91) of HD patients. The rationale for enrolling new HD patients are: 1) they will not have already experienced the executive function decline associated with HD; 2) there is a high dementia incidence even within the first year of HD; 3) survival bias is present when studying prevalent HD patients; and 4) we want to intervene before the neurodegenerative process begins.

Inclusion Criteria:

Participants must be:

- Within 3 months to 3 years of initiating HD
- 18 years or older at enrollment
- English-speaking

- Willing to participate in research

Exclusion Criteria:

Patients with the following conditions will not be included in the study:

- Pregnancy
- Angina pectoris
- Chronic lung disease requiring oxygen
- Musculoskeletal conditions that limit mobility
- Upper or lower extremity amputation
- Orthopedic disorders exacerbated by physical activity
- Femoral arteriovenous (AV) access
- Blindness/ Legal blindness
- Hepatitis B infection
- Inability to recognize letters and numbers

In addition to patients with these conditions, patients who are currently incarcerated will be excluded from the study.

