All potential female participants of childbearing age will be asked if they are currently pregnant during initial contact by a study team member to introduce the study.

Recruitment/Enrollment: We will recruit approximately 200 adult ESRD patients from Fresenius Kidney Care Hemodialysis Centers and DaVita Dialysis centers located in the greater Baltimore, Maryland area, where we expect 240-250 eligible participants will be receiving HD. The treating provider at the HD center will be required to approve that it is safe for the patient to enroll.

Participating Dialysis Centers:

Fresenius Kidney Care Centers: Fresenius Kidney Care Caroline Street, Fresenius Kidney Care Broadway Street, Fresenius Kidney Care Merritt Boulevard of Dundalk, Fresenius Kidney Care Fleet Street, Fresenius Kidney Care Nashua Court, Fresenius Kidney Care Dundalk, Fresenius Kidney Care Cross Keys, Fresenius Kidney Care White Marsh, Fresenius Kidney Care Anne Arundel, Fresenius Kidney Care Greenspring Drive (Lutherville-Timonium)

DaVita Dialysis Centers: DaVita Downtown Dialysis, DaVita 25th Street Dialysis, DaVita Greenspring Dialysis, and DaVita Good Samaritan Dialysis

Recruitment/Enrollment at Fresenius Kidney Care Centers:

We have obtained a HIPAA waiver to access patient medical records so we may generate a list of potential participants and check for eligibility. The PI/Project Manager/Study Coordinator, or Frenova staff will access the Fresenius Kidney care electronic medical records to identify eligible participants. Additionally, we will provide the clinics with our study brochure for distribution to patients to inform them of the study. If they are interested in hearing more about the study, they may contact us directly. All patients at participating Fresenius dialysis centers who meet eligibility criteria will be contacted either by phone or in person by a research assistant to describe the study. If they are interested in participating in the study and agree to participate, they will provide informed consent and enrolled.

Recruitment/Enrollment at DaVita Dialysis Centers:

The DaVita nephrologist/nurse practitioner will identify potential participants and establish eligibility. All patients who meet the eligibility criteria will be contacted by the DaVita nephrologist/nurse practitioner to

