introduce the study and ask if they are interested in learning more. If the patient agrees and would like more information about the study, the nephrologist/nurse practitioner will ask them to sign a DaVita “HIPAA Authorization to Use and Disclose Information for Research Purposes” form so their information may be shared with our study team and we can provide them with more information about the study. DaVita will provide the Program Manager with a list of eligible potential participants with signed DaVita HIPAA authorization forms. Our research team will contact patients on the list either by phone or in-person to discuss the study and if they are interested and agree to participate, they will provide informed consent and enrolled.

Participants will be enrolled at 4 locations in New York City: The Lower Manhattan Dialysis Center 1, The Lower Manhattan Dialysis Center 2, River Renal Services, Inc. and Chinatown Dialysis Center, LLC. The NYU Langone Health study team will analyze and collect data for this study.

Timeline: We will administer the interventions in two waves. In wave 2 (2 years after the start of the study), we will return to the dialysis centers in the first wave and begin enrollment again. This will allow us to identify new HD patients at each center. We will allow 1 month for identification of participants, initial contact by a research assistant, and baseline assessment as described below. Participants will be followed for 1 year after the end of the intervention for mortality and hospitalization.

Randomization:

We will randomize participants after completion of the baseline assessments. Participants will be block randomized (i.e., stratified over time) and stratified by sex, race/ethnicity, and dialysis center. They will be randomly assigned to one of the four study arms using a blind and secure computer based allocation system: **a) 6 months of CT alone, b) 6 months of ET alone, c) 6 months of CT+ET, d) standard of care.** We will use block sizes of four to ensure desired sizes in each arm. Given the nature of our interventions, it is not possible to blind the participant, treating provider and other HD center staff.

Intradialytic Interventions to Preserve Executive Function:

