Participants randomized to either CT or ET will engage in the activity for a minimum of 30 minutes during each HD session. After 15 minutes on HD, the research assistant will approach the participant to initiate the intervention. For those in the CT+ET arm, participants will start with 30 minutes of CT, followed by a 15-minute break, and then 30 minutes of ET. Participants will be allowed to continue with their assigned intervention for longer if needed.

A research assistant will be on site throughout the duration of the interventions to set up tablets and foot peddlers, assist participants if needed, monitor safety related to intervention arms, and collect tablets and foot peddlers after participant have completed their assigned intervention for the day. Any safety concerns will be recorded and reported immediately to the Principal Investigator.

Disinfection Protocol:

iPads/Tablets: iPad devices can only be used in the patient treatment area with a protective cover that can be disinfected. iPad devices will be disinfected before leaving the patient's chairside and before being placed back into the storage unit to be recharged. It must be disinfected before being provided to another patient. iPad devices should be cleaned with a soft cloth dampened with an EPA registered tuberculocidal "hospital disinfectant" or a 1:100 dilution of bleach (300-60 mg/L free chlorine). A saturated cloth MUST NOT be used to clean the device; wring out excess solution so the cloth is dampened, not saturated. Any blood or body fluid contamination should be cleaned immediately. The cover should be removed, and both the cover and device cleaned thoroughly. Do not use window cleaners, household cleaners, aerosol sprays, solvents, alcohol, ammonia or abrasives on the iPad device itself. After use, all equipment and supplies must be considered as potentially blood contaminated, and should be separated, handled with caution and either disinfected or discarded.

Alcohol products shall not be used to disinfect large environmental surfaces. When mixing bleach solutions, staff must wear personal protective equipment (PPE), including disposable gloves, face shield or eye protection with full side shields and fluid-resistant gowns.

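### A single block size of four for four arms lets unblinded clinicians who screen and approve patients deduce some allocations in advance

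*Combined protocol and SAP*

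**What the plan says.** Study Procedures sets out the design: "We will randomize participants to CT alone, ET alone, both CT+ET, or SC resulting in four arms". The power section implies equal allocation, with a target "from which we will need to recruit 50 per arm".

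The protocol's Randomization section gives the method: "Participants will be block randomized (i.e., stratified over time) and stratified by sex, race/ethnicity, and dialysis center". It adds: "We will use block sizes of four to ensure desired sizes in each arm". No second block size is mentioned, and nothing says the size is withheld from the centres. The same section provides for a blind and secure computer system, used after the baseline assessment, and concedes that "it is not possible to blind the participant, treating provider and other HD center staff".

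Study Procedures describes the method more loosely: "Randomization will be achieved through balancing methods over the three stratification factors".

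Under Recruitment/Enrollment, the treating provider must confirm that enrolment is safe for each patient. At DaVita centres the nephrologist or nurse practitioner identifies patients, establishes eligibility and makes first contact. At Fresenius centres eligible patients "will be contacted either by phone or in person by a research assistant to describe the study". Once treatment starts, "the research assistant will approach the participant to initiate the intervention".

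The updated statistical methods at the end of the document report that 121 participants were block-randomized by sex, race and dialysis centre with a secure system in R. They do not give the block size used.

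**The concern.** A secure system hides the list, but it cannot hide what follows from the rule that made the list. With four arms and blocks of four, each block is one ordering of the four arms. The strata are made of things staff can see: centre, sex and race/ethnicity. The arms are visible too, since a participant has a tablet, a pedaller, both or neither. A clinician who remembers the last few patients of a given type at the centre can narrow down the next assignment.

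What matters is who can use that knowledge before randomization. The treating provider's safety approval and the DaVita clinicians' eligibility judgement both come before it, and both are made by people the plan says cannot be blinded. If a fitter or keener patient is put forward when an exercise slot is due, and held back otherwise, the comparison of active arms with standard of care carries a selection bias. Masked outcome assessors do not remove it, because it arises before any outcome is measured. With about 30 participants per arm (121/4), a few steered patients could matter.

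**Working it through.** **The plan's own figures.** Target of 47 analysable per arm and 6% attrition: 47/(1 − 0.06) = 50 per arm; 4 × 50 = 200; 200/16 centres = 12.5, the plan's approximate 13 per centre. These reproduce. The documents give no figure for predictability.

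**A complete block.** The best guess at positions 1 to 4 is right with probability 1/4, 1/3, 1/2 and 1. The mean is (1/4 + 1/3 + 1/2 + 1)/4 = 52.1%, against 25% by chance, and one allocation in four is certain. For the yes/no question of whether the next patient will exercise (ET or CT+ET), the probabilities are 1/2, 2/3, 2/3 and 1, with a mean of 70.8% against 50% by chance; (1/3 + 1)/4 = 33.3% of these calls are certain.

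**Incomplete strata.** Few strata fill whole blocks, so the complete-block figures overstate the exposure. For a stratum of n participants, let q be the whole part of n/4 and r the remainder. Certain allocations number q. Expected correct guesses are q × (1/4 + 1/3 + 1/2 + 1) plus the first r of those terms. A stratum of three, for example, has no certain allocation and a mean guess of (1/4 + 1/3 + 1/2)/3 = 36.1%.

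Stratum sizes were simulated with a 50/50 sex split. The documents do not give the number of race/ethnicity levels, so two to four equal groups were assumed. With equal centres:

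| Participants / centres | Race groups | Strata | Mean per stratum | Certain | Best guess right |
|---|---|---|---|---|---|
| 200 / 16 | 2 | 64 | 3.1 | 12.6% | 42.1% |
| 200 / 16 | 3 | 96 | 2.1 | 7.6% | 37.5% |
| 200 / 16 | 4 | 128 | 1.6 | 4.7% | 34.3% |
| 121 / 15 | 2 | 60 | 2.0 | 7.2% | 37.1% |
| 121 / 15 | 3 | 90 | 1.3 | 3.5% | 32.9% |
| 121 / 15 | 4 | 120 | 1.0 | 1.9% | 30.6% |

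Uneven centre sizes raise the upper end to about 14% certain and 43% correct at 200/16, and to about 10% and 40% at 121/15.

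The documents give several centre counts: 13 in Study Population, 16 in the power section, and 18 if the 14 Baltimore and 4 New York sites are added. With 200 participants and equal centres, 13 to 18 centres gives 15% down to 4% certain and 44% down to 33% correct.

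**Does the small block deliver its stated purpose?** At 200/16, about 49 to 95 of the 64 to 128 strata end with an incomplete block. Blocks of four within these strata therefore do not by themselves secure equal arms, and little balance is lost by changing them.

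**Effect of mixed blocks.** Take sizes drawn at random from 4 and 8, and a guesser who knows those are the two possible sizes. In a stratum of 4, certain allocations fall from 25% to 0 and the mean guess from 52.1% to 41.8%. In a stratum of 8, they fall from 25% to 6.0% and from 52.1% to 47.2%. Over the simulated strata with two or three equal race/ethnicity groups, certain allocations fall to about 0–1.4%.

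**The case against.** The strongest reply is that the plan leaves little room to steer. All patients meeting the criteria are to be contacted, at Fresenius and at DaVita centres. The protocol expects 240–250 eligible patients and assumes 88% consent: 0.88 × 240 = 211 and 0.88 × 250 = 220, for a target of 200. A month is allowed for identification, contact and baseline assessment, during which other patients may be randomized and upset a prediction. The updated methods adjust the main comparison for age, education and the baseline value of the outcome, which would absorb part of any steering by fitness. If blocks restart with each enrolment wave, which the protocol does not say, certain allocations fall to about 1–9% (200) or 0.3–5% (121).

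This limits the risk without closing the route. The rule to contact everyone applies only after clinicians have judged eligibility, and the safety approval is itself a judgement. The order in which patients come forward also remains open, and in a small stratum order decides the arm. Adjustment cannot reach unmeasured motivation or fitness.

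Two stronger readings are tempting, and the documents support neither. A reader might infer that allocation is not concealed. The protocol does specify a blind and secure system used after baseline assessment; the weakness is that the block rule can defeat it for a minority of allocations. A reader might also infer that unblinded staff who recruit run the randomization. No section names the system's operator or says that the research assistants who recruit are those who deliver; the updated methods say only that assessors and deliverers were separate teams. The point rests on treating providers and DaVita clinicians alone.

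The Study Procedures wording on balancing is generic and could describe stratified blocks. It calls for alignment and is not evidence of a second scheme.

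**Conclusion.** The point holds as a moderate, inexpensive weakness. One block size of four for four equal arms makes some allocations foreseeable to unblinded clinicians who have a say in who enrols. The size is about 5–14% of allocations certain as planned (200/16) and about 2–10% for the trial as run (121/15), with the best guess right 34–43% and 31–40% of the time against 25% by chance. The 52% figure applies only to complete blocks and should not be quoted for the trial as a whole.

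These are upper-end exposures, because they assume an observer who recalls every earlier allocation in the stratum and that participants are randomized one at a time. The figures for the 121 also assume that blocks of four were used as planned, which the updated methods do not confirm. No bias in the treatment effect has been estimated, and nothing in the documents shows that steering took place.

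**What to change.** In the protocol's Randomization section, replace the single block size with sizes drawn at random from 4 and 8. State that the sizes are withheld from anyone who screens, approves, recruits or delivers, and name the role that operates the allocation system. Reword the sentence on balancing in Study Procedures so that both sections describe the same scheme.

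The cost is a small change to a program that is already computer-based and a short protocol edit. The downside is slightly more imbalance within strata and in arm totals. Mixed blocks reduce predictability but do not bring it down to chance.

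The 121 participants are already randomized and the trial has been terminated, so for them the remedy is reporting: give the block size or sizes used, say whether blocks restarted by wave, say who operated the system and who knew the block size, and list predictability as a limitation.
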